Note to File

Study Title: An Open-Label Tolerability and Efficacy Study of ZYN002 Administered as a Transdermal Gel to Children and Adolescents with 22q11.2 Deletion Syndrome

Protocol Number: ZYN2-CL-031.05

Compound: ZYN002

Sponsor Name: Harmony Biosciences

Legal Registered Address: [name]
[name]
USA

Statistical Analysis Plan Date: 25 May 2022

Description: Dosing was adjusted based on weight. Therefore, the decision was made to collect data as a single arm ("ZYN002") instead of by dose or by period because the dosing is not relevant to the interpretation of the study results and based on pharmacokinetic modeling, exposure is consistent across doses. The Protocol and Statistical Analysis Plan will not be updated. Instead, this Note to File has been written to state how data were collected.

Effective Date: 16 February 2026

Sponsor Signatory:

PPD

16 Feb 2026

PPD

Date

Executive Director, Regulatory Medical Writing
Harmony Biosciences
[name]
[name]

Confidentiality Statement

This document contains confidential information of Harmony Biosciences.
Do not copy or distribute without prior written permission of the Sponsor.
Any unauthorized use, reproduction, publication, or dissemination is strictly prohibited.

STATISTICAL ANALYSIS PLAN

ZYN002 Cannabidiol (CBD)

Protocol Number: ZYN2-CL-031.05

An Open-Label, Tolerability and Efficacy Study of ZYN002 Administered as a Transdermal Gel to Children and Adolescents with 22q11.2 Deletion Syndrome (INSPIRE)

Sponsor:

Zynerba Pharmaceuticals Pty., Ltd.
[name]

Zynerba Pharmaceuticals Pty., Ltd.
[name]
Suite 300
[name]

IND Number:	130876
Date of Plan:	25 May 2022
Based on:	Protocol Version Amendment 05 Dated: 17 August 2022
Based on:	CRF Version Date: 01 November 2021

CONFIDENTIAL INFORMATION

The information contained in this document is the property of Zynerba Pharmaceuticals Pty., Ltd. (Zynerba) and is confidential. It is intended solely for the use of Zynerba employees and contracting consultants and regulatory agencies. Reproduction or disclosure of the information contained herein in whole or in part is forbidden to persons not involved in the clinical investigation of Zynerba, unless such persons are bound by a confidentiality agreement with Zynerba.

SIGNATURE PAGE

This document has been reviewed and accepted by:

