4. STUDY DESIGN

This is an open-label study to assess the safety, tolerability and efficacy of CBD administered as ZYN002, a transdermal gel, for the treatment of child and adolescent patients with 22q. Male and female patients with 22q will be treated in Period 1 for 14 weeks.

Patients with less than a 25% improvement from baseline in the ABC-C Irritability subscale may have their total dose increased by the investigator at Week 6.

Patients that have made a $\geq 35\%$ improvement on the ABC-C Irritability sub-scale will be allowed to continue to Period 2 for an additional 24 weeks of treatment. Only patients taking AED medications for treatment of seizures or epilepsy will have an additional one or two-week Taper Period.

Approximately 20 male and female patients, ages 4 to < 18 years, will receive ZYN002.

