8. SAFETY ANALYSES

The safety analysis set will be used for all safety analyses. Study drug administration, AEs and concomitant medications will be summarized by treatment period (Period 1, 2, and overall).

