8.1.1. Adverse Events

All adverse events will be coded using the Medical Dictionary for Regulatory Activities (MedDRA) Version 21.0 or greater. Treatment emergent adverse events (TEAEs) are defined as adverse events with onset dates on or after the first dose of study drug.

All AE summaries will include total number of TEAEs and total number of patients with AEs.

An overall summary of adverse events will include number (%) of patients reporting ≥ 1 TEAE (and number of TEAEs), TEAE by Severity (and number of TEAEs), treatment-related TEAEs (and number of TEAEs), SAEs (and number of TEAEs), TEAE by outcome (and number of TEAEs), TEAEs that resulted in treatment discontinuation (and number of TEAEs). In addition, the total number of TEAEs by subject will be summarized.

Additionally, summaries will be presented for all TEAEs by system organ class and preferred term (overall and by severity). TEAEs determined by the investigator to be treatment-related (overall and by severity). Serious AEs will also be summarized. Adverse events causing permanent discontinuation from treatment will be summarized, fatal adverse events will be summarized, and TEAEs by preferred term in descending order will be summarized.

The incidence of adverse events will be summarized using descriptive statistics by system organ class and preferred term. Patients are counted only once in each system organ class category, and only once in each preferred term category. Treatment-related adverse event summaries will include adverse events with missing relationship to study drug. For the summaries by severity, patients and TEAEs are counted at the greatest severity.

AEs will be summarized separately for each treatment Period (1, 2) and overall (the whole study).

Listings for fatal AEs, serious AEs, and AEs leading to discontinuation, will also be presented.

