8.1.8. Patient Skin Irritation Score

The total number of patient skin irritation scores (0=No Skin redness to 4=Intense Redness with Blisters or Broken Skin) collected from the diary will be displayed within each treatment period overall and within 2-week intervals. The number of subjects with an assessment overall and within each 2-week period will be summarized. In addition, the total number of unique subjects for each category will be displayed.

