11. LIST OF SUMMARIES AND LISTINGS

Summary Number	Title	Population	Period 1 Display
14.1.1	Summary of Patient Disposition	Enrolled	X
14.1.2	Summary of Demographics	Safety Analysis Set	X
14.1.3	Summary of Baseline Characteristics	Safety Analysis Set	X
14.1.4	Summary of Medical History	Safety Analysis Set	X
14.1.5	Summary of Prior Medications by Therapeutic Class and Preferred Term	Safety Analysis Set	X
14.1.6	Summary of Electrocardiogram Findings at Baseline	Safety Analysis Set	X
14.1.7	Summary of Physical Examination Findings at Baseline	Safety Analysis Set	X
14.1.8	Summary of Neurological Examination Findings at Baseline	Safety Analysis Set	X
14.2.1	Summary of Change from Baseline to Weeks 6, 14, 22, 30, and 38 in the ABC-C Checklist	mITT Analysis Set	X
14.2.2	Summary of 25% and 50% responders at Weeks 6, 14, 22, 30, and 38 in the ABC-C Checklist	mITT Analysis Set	X
14.2.3	Summary of Change from Baseline to Weeks 6, 14, 22, 30, and 38 in the ADAMS Checklist	mITT Analysis Set	X
14.2.4	Summary of Change from Baseline to Weeks 6, 14, 22, 30, and 38 in the CGI-S Scale	mITT Analysis Set	X
14.2.5.1	Summary of CGI-I at Baseline, Weeks 6, 14, 22, 30, and 38	mITT Analysis Set	X
14.2.5.2	Shifts from Baseline to Weeks 6, 14, 22, 30, and 38 in CGI-I	mITT Analysis Set	X
14.2.6.1	Summary of Change from Baseline to Weeks 6, 14, 22, 30, and 38 in the PARs-R Scale	mITT Analysis Set	X
14.2.6.2	Summary of Shifts from Baseline to Weeks 6, 14, 22, 30, and 38 in CGI –I Categories (≤ 52 and > 52)	mITT Analysis Set	X
14.3.1.1.1	Summary of Sachet Information (Period 1)	Safety Analysis Set	X
14.3.1.1.2	Summary of Study Drug Duration (Period 1)	Safety Analysis Set	X
14.3.1.2.1	Summary of Sachet Information (Period 2)	Safety Analysis Set	
14.3.1.2.2	Summary of Study Drug Duration (Period 2)	Safety Analysis Set	
14.3.1.3.1	Summary of Sachet Information (Overall)	Safety Analysis Set	
14.3.1.3.2	Summary of Study Drug Duration (Overall)	Safety Analysis Set	
14.3.2.1.1	Overall Summary of Treatment Emergent Adverse Events (Period 1)	Safety Analysis Set	X
14.3.2.1.2	Overall Summary of Treatment Emergent Adverse Events (Period 2)	Safety Analysis Set	
14.3.2.1.3	Overall Summary of Treatment Emergent Adverse Events (Overall)	Safety Analysis Set	
14.3.2.2.1	Summary of Treatment Emergent Adverse Events by System Organ Class, and Preferred Term (Period 1)	Safety Analysis Set	X

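### The Note to File sets aside the period split for reasons that concern only dose; if it governs reporting, cumulative safety summaries mix up to 14 and up to 38 weeks of follow-up

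*SAP*

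**What the plan says.** The Note to File at the front of the SAP records a decision to collect data as a single ZYN002 arm "instead of by dose or by period because the dosing is not relevant to the interpretation of the study results". It adds that "based on pharmacokinetic modeling, exposure is consistent across doses", and that "The Protocol and Statistical Analysis Plan will not be updated".

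The SAP body, dated 25 May 2022, plans otherwise:

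- Section 8: "Study drug administration, AEs and concomitant medications will be summarized by treatment period (Period 1, 2, and overall".
- Section 8.1: sachets dispensed and returned, and treatment duration, overall and for each period.
- Section 8.1.1: "AEs will be summarized separately for each treatment Period (1, 2) and overall (the whole study".
- Section 8.1.7: the same split for concomitant medications.
- Section 8.1.8: diary skin scores "will be displayed within each treatment period overall and within 2-week intervals".
- Section 11: separate Period 1, Period 2 and overall tables for exposure and for the adverse-event summaries, for example "Overall Summary of Treatment Emergent Adverse Events (Period 2".

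On design, SAP Section 4 states: "Male and female patients with 22q will be treated in Period 1 for 14 weeks". Patients with at least a 35% improvement in ABC-C irritability may continue for another 24 weeks. The footnotes to the Period 1 schedule end the study at Week 14 for patients who do not qualify.

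**The concern.** Both reasons in the Note are about dose. Neither bears on period, which separates a 14-week window that every treated patient enters from an extension open only to patients selected on an efficacy score. As written, the Note and the SAP disagree on how safety, the primary objective, is to be presented, and no reason is given for the part of the change that concerns period.

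At stake are the summaries that accumulate over time: adverse events, drug exposure, concomitant medications and diary skin scores. With only a pooled column, one patient has up to 14 weeks in which to have an event and another has up to 38. The mix is set largely by who met the irritability criterion. An incidence of that kind is neither a 14-week nor a 38-week risk, and it is hard to set beside the sponsor's 12-week studies described in protocol Section 5.3.2.

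**Working it through.** The plan gives no rate, power or sample-size figure on this point, so there is nothing to reproduce. The calculation below is an illustration.

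**Inputs from the documents.** Period 1 is 14 weeks and Period 2 adds 24, so 38 in total. About 20 patients are planned (SAP Section 4). The safety denominator is all patients with at least one dose (SAP 6.4.1).

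**Assumed inputs.** The documents give none of these for this trial.

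- p14, the 14-week risk of a first event: 20%, with 10% as a second case.
- f, the share entering Period 2: 25%, 50% or 75%.
- h, the Period 2 hazard as a multiple of the Period 1 hazard: 1, 0.5 or 0.

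Dropout and taper weeks are ignored.

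**Follow-up.** Mean weeks per patient = 14 + 24f, which gives 20, 26 and 32. The share of person-time from Period 2 = 24f / (14 + 24f): 6/20 = 30%, 12/26 = 46% and 18/32 = 56%.

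**Incidence.** The 38-week risk is p38 = 1 − (1 − p14)^(1 + h × 24/14). With h = 1 the exponent is 38/14. The pooled figure is (1 − f) × p14 + f × p38.

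For p14 = 20%:

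- h = 1: p38 = 1 − 0.80^(38/14) = 45.4%
- h = 0.5: p38 = 1 − 0.80^(1 + 12/14) = 33.9%
- h = 0: p38 = 20%

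| Period 2 hazard | f = 25% | f = 50% | f = 75% |
|---|---|---|---|
| Same as Period 1 | 26.4% | 32.7% | 39.1% |
| Half of Period 1 | 23.5% | 27.0% | 30.4% |
| No first events | 20.0% | 20.0% | 20.0% |

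Example for the first cell: 0.75 × 0.200 + 0.25 × 0.454 = 0.264.

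For p14 = 10% under a constant hazard, p38 = 24.9% and the pooled figures are 13.7%, 17.4% and 21.2%.

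**With the split kept.** Period 1 returns p14 on all 20 patients whatever f is. Period 2 is reported on its own entrants: 5, 10 or 15 patients for the three values of f.

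**Are late events plausible?** In the sponsor's open-label Fragile X study (protocol Section 5.3.2), 33 treatment-emergent events were reported in the 12-week period and 66 in total through Week 51. These are event counts, not first-event risks, so they show that events continue but do not fix h.

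**The case against.** Several stronger readings are tempting, and the documents do not support them.

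- **The period tables have been withdrawn.** The Note speaks of how data were collected and names no table as cancelled. The SAP's period commitments remain in force on paper. What stands is a conflict: setting the single arm against a period split reads naturally as dropping that split, and the Note does not say whether the tables will be produced.
- **The only all-patient 14-week safety estimate is lost.** SAP 5.1 plans a separate Period 1 analysis that includes adverse events, with table release estimated for 10 June 2022, and Section 11 marks the Period 1 adverse-event tables for it. Those displays may exist. The Note does not mention them, and the documents do not show whether they were produced or will appear in the final report.
- **A pooled column is post hoc.** It is not. SAP 8, 8.1.1 and Section 11 plan overall tables with this same blend, and the objective covers up to 38 weeks. Protocol 13.5 plans adverse events by dose and overall, with no period split. What could be lost is the period tables that sit beside the overall ones.
- **All safety data are blended.** Vital signs, ECG, laboratory results and investigator skin scores are planned by visit and are unaffected if visits are kept.
- **The decision was taken years after lock.** From the estimated lock of 14 December 2022 to the Note's date is 1,160 days, but the lock date is an estimate and the Note does not date the decision.

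The size is also fairly challenged: all three drivers of the illustration are assumed, and with no first events in Period 2 the distortion vanishes. None of this supplies a reason for setting period aside.

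**Conclusion.** The concern holds in a conditional form. The Note conflicts with SAP 8, 8.1, 8.1.1, 8.1.7 and the Section 11 tables, and its reasons do not reach period. If it governs reporting, the cumulative summaries in the final report are left only in pooled form.

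On the assumptions shown, a 20% 14-week risk could be reported as anything from 20% to about 39%. The direction, a pooled figure at or above the 14-week risk, does not depend on those assumptions; the size does. The mix also depends on dropout and on families choosing to continue, although the irritability criterion is the only planned rule. Because that criterion selects improvers, late-event rates in the extension cannot be read as rates for all treated patients.

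This should be corrected, since it bears on how the primary objective is read. It does not show that any result is wrong.

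**What to change.** Reissue the Note with the words *or by period* struck. Then produce the Period 1, Period 2 and overall exposure and adverse-event tables already listed in SAP Section 11, each with one ZYN002 column and with Period 1 as the all-patient readout. The single-arm decision is untouched: SAP 5.2 already specifies one ZYN002 column for the Period 1 analyses.

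For concomitant medications, add the period split to Table 14.3.7, because SAP 8 and 8.1.7 require it and Section 11 lists that table without it. Keep the per-period display of diary skin scores required by 8.1.8.

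Leave the overall tables as planned, without a post hoc label. If the sponsor does intend to omit the period tables, that omission is the departure to document, with a reason specific to period.

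The cost is one reissued paragraph and one added split. The exposure and adverse-event tables are already specified.

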7.3. Dose Rationale

Steady-state CBD concentrations were simulated, using a nonlinear mixed effects model (NONMEM, n=1000), for pediatric subjects by age group and by body weight. Simulated exposures were compared, for each pediatric age group receiving ZYN002 at either 125 or 250 mg CBD BID, to adults receiving ZYN002 250 mg CBD BID (a ZYN002 dose that has been demonstrated to be safe and well tolerated; Section 5.3), assuming dose proportionality. The simulations suggest that dosing 125 mg CBD BID in subjects weighing ≤ 35 kg results in relatively similar mean AUCs (85-140%) compared to adults receiving 250 mg CBD BID and that dosing pediatric age groups weighing > 35 kg with 250 mg CBD BID also results in similar mean AUCs (96 to 123%) compared to adults.

Therefore, a total daily dose of 250 or 500 mg CBD will be applied to patients that weigh ≤ 35 kg and a total daily dose of 500 or 750 mg will be applied to patients that weigh > 35 kg.

ZYN002 studies have been conducted in healthy subjects and patients using the CBD 4.2% concentration at similar daily dose levels as this study (250, 500 and 1000 mg/day). ZYN002 has shown to be safe and well tolerated in all studies (Refer to Section 5.3).

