7.5. Dose Adjustment Criteria

Patients will receive their assigned dose of ZYN002 as described in Section 7.4. Dose adjustments will be made for patients on AEDs for treatment of seizures or epilepsy, who will have a Taper Period at the end of the study, unless they are transitioning to receive drug through Special Access, if available (Section 7.8).

Should the weight of the patient change from visit to visit the dose may be adjusted, at the discretion of the investigator.

In addition, at Week 6 if the patient has less than a 25% improvement from baseline in the ABC-C irritability subscale, the investigator may increase the total daily dose.

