13.5. Statistical Methods

Descriptive statistics (mean, median, standard deviation, minimum, and maximum) for continuous data and number (n) and percentage (%) for categorical data will be presented for all efficacy and safety parameters.

All efficacy assessments will be summarized at Weeks 6, 14, 22, 30, and 38.

Vital sign assessments (actual and change from screening) taken at study Day 1, Weeks 6, 14, 22, 30, and 38 will be summarized using descriptive statistics and presented by maintenance dose.

ECGs (actual and change from Screening) will be summarized by actual treatment group. ECG results including any clinically significant findings will be summarized at each study visit.

Safety laboratory and urinalysis assessments taken at Week 6, 14, and Week 38 (actual and change from screening) will be summarized by treatment at the time of the assessment.

Application site irritation will be summarized using counts and percentages for each respective site irritation score (0, 1, 2, 3, or 4) by dose at the time of assessment.

AEs will be tabulated by the actual treatment dose of study drug received at the time of initiation of the adverse event and classified by system organ class and preferred term using the Medical Dictionary for Regulatory Activities (MedDRA). Additionally, AEs will be tabulated overall (total number of AEs and total number of patients with AEs).

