5.2. Data included in Period 1 Analyses

The records to be included in the Period 1 analyses will include all records with a nominal visit of ≤ 4 (Week 14/ET). All summaries will include one column only identified as ZYN002.

In an attempt to include all Period 1 Concomitant Medications and Adverse Events in the Period 1 analyses TGG will need to calculate a Week 14 Date for both subjects who completed Period 1 and who discontinued in Period 1 before Week 14. This will be accomplished by the following steps using the last non-missing value as the actual or imputed Week 14 date:

- a) If a subject completes Period 1 then use their actual Week 14 Date.
- b) If a subject discontinues before Week 14 date and their last nominal visit is identified as Week 14/ET then add ‘X’ days to that date to get to Day 98 (7 times 14).
- c) If Week 6, TGG will impute the Week 14 cutoff date to be the Week 6 date plus (7 times 8) to get the Week 14 imputed Date

d) If Day 1, TGG will impute the Week 14 date to be Day 1 plus (7 times 14)

Treatment emergent adverse events and concomitant medication summaries will include start dates that occur any time before treatment begins and treatment ends. Refer to [Section 6.2.3](#).

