10. CHANGES FROM THE PROTOCOL

None identified.

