14.3.8.1	Summary of Patient Monthly Skin Irritation Scores	Safety Analysis Set	
14.3.8.2	Summary of Investigators Skin Irritation Scores at Each Visit	Safety Analysis Set	
14.3.9	Summary of Columbia Suicide Severity Rating Scale Children's Version Positive Ratings	Safety Analysis Set	
14.3.10	Summary of Trough Plasma Concentrations for Anti-Epileptic Drugs at each Sampling Time (Weeks 6, 14, and 38)	PK Analysis Set	
14.3.11	Summary of CBD and THC Plasma Levels at Each Visit by Dose	Safety Analysis Set	

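### The Note to File pools all doses because exposure is said to be consistent, but the modelling in the protocol is reported for the starting doses only and implies 1.5- to 2.0-fold higher exposure after a Week 6 increase

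*SAP*

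**What the plan says.** **Pooling decision.** The Note to File (effective 16 February 2026) says that dosing was adjusted by weight and that for this reason "the decision was made to collect data as a single arm ('ZYN002') instead of by dose or by period". The scientific ground given is that "the dosing is not relevant to the interpretation of the study results and based on pharmacokinetic modeling, exposure is consistent across doses". It adds that neither the protocol nor the SAP will be revised.

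**Modelling.** Protocol Section 7.3 says that 125 mg BID at ≤35 kg "results in relatively similar mean AUCs (85-140%) compared to adults receiving 250 mg CBD BID". For 250 mg BID above 35 kg it gives 96 to 123%. The comparison assumes dose proportionality.

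**Dosing.** Under Protocol Section 7.4, patients start on 250 mg/day (≤35 kg) or 500 mg/day (>35 kg), and these may rise to 500 and 750 mg/day. Section 7.5 makes the rise available, at the investigator's choice, "at Week 6 if the patient has less than a 25% improvement from baseline in the ABC-C irritability subscale". Both sections also allow adjustment if weight changes between visits.

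**Displays.** Protocol Section 13.5 states that "AEs will be tabulated by the actual treatment dose of study drug received at the time of initiation of the adverse event". It also asks for skin irritation scores by dose at assessment and laboratory results by treatment at assessment. The synopsis reproduced in the SAP repeats all three. The SAP's own safety sections differ:
- Section 8.1.1 splits adverse events by period and overall.
- Section 8.1.6 gives laboratory results by visit.
- Section 8.1.8 gives diary skin scores by period and two-week interval.
- Section 8.1.9 gives investigator skin scores by body site.
- For Period 1, Section 5.2 says "All summaries will include one column only identified as ZYN002".
- Section 8.1.12 combines all patients for CBD troughs, whereas Table 14.3.11 is titled "Summary of CBD and THC Plasma Levels at Each Visit by Dose".
- Section 10, on changes from the protocol, reads "None identified".

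**The concern.** Safety and tolerability are the primary objective. If exposure rises materially after Week 6 in some patients, events that begin at the higher dose are mixed with time at the lower dose and with patients who were never increased. A table with no dose split cannot show that. The Note replaces the split that the protocol called for with a factual statement about exposure, so the statement has to be right. It also describes dosing as a matter of weight and leaves out the response trigger. The patients at the raised doses are thus a selected group, and a reader of the pooled tables would not learn this.

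**Working it through.** **Inputs.** The AUC ranges and the proportionality assumption come from Protocol Section 7.3, and the dose levels and sachet counts from Section 7.4. The AUC ranges are outputs of a population PK model whose parameters are not given. They cannot be reproduced and are taken as stated. The sachet arithmetic does check: 2.98 g × 4.2% = 125.2 mg of CBD per sachet.

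**What is reported.** Section 7.3 says that 125 and 250 mg BID were simulated, but it gives a result only for each weight band's starting dose. It reports none for 250 mg BID at ≤35 kg, and 375 mg BID is not among the doses named as simulated.

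**Step 1: exposure after the increase.** Raised mean AUC = stated mean AUC × (raised dose / starting dose).

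| Weight | Daily dose | Factor | Mean AUC, % of adult 250 mg BID |
|---|---|---|---|
| ≤35 kg | 250 mg | 1 | 85–140 (stated) |
| ≤35 kg | 500 mg | 500/250 = 2.0 | 170–280 |
| >35 kg | 500 mg | 1 | 96–123 (stated) |
| >35 kg | 750 mg | 750/500 = 1.5 | 144–184.5 |

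A patient who is increased therefore moves 2.0-fold or 1.5-fold at Week 6.

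**Step 2: spread across what is pooled.**
- Starting doses only: 140/85 = 1.65-fold.
- All doses: 280/85 = 3.29-fold. This is 1.65 × 2.0, so it contains the spread already present before any increase.
- One nominal dose, 500 mg/day: 170–280% at ≤35 kg against 96–123% above 35 kg, a ratio between 170/123 = 1.38 and 280/96 = 2.92. Dose alone is not a sufficient label, and weight group is needed beside it.

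**Step 3: local tolerability.** An increase takes each application from one sachet to two, or from two to three. Plasma AUC does not address skin irritation from more gel, so even uniform systemic exposure would not justify pooling skin scores.

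**Step 4: whether the period split helps.** Week 6 lies inside Period 1, which runs to Week 14. A Period 1 column mixes time before and after the increase, and a Period 2 column can mix raised and unraised patients. The Note sets this split aside as well.

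**Step 5: how much dilution is possible (illustration).** The documents give neither event rates nor the number increased. Assume 10% of patients have an event at a starting dose and 30% at a raised dose, with a share f increased. The pooled rate is 0.10(1 − f) + 0.30f:
- f = 0.25: 0.075 + 0.075 = 15%
- f = 0.50: 0.05 + 0.15 = 20%
- f = 0.75: 0.025 + 0.225 = 25%

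A threefold difference would appear as one figure between 15% and 25%.

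**The case against.** The strongest reply is that the Note refers only to PK modelling and names no section. The synopsis plans a comparison of observed concentrations with population PK simulations, and the Note is dated more than three years after the planned release of final tables (31 January 2023, SAP Section 5.3). It may rest on later results that are not in these documents. That stands, and it limits the conclusion to the modelling that can be seen here. The raised-dose ranges above are likewise extrapolations, not simulated values.

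Four stronger readings are tempting and should not be drawn:
- *That the Week 6 increase produces a 3.3-fold rise.* It does not. That figure sets the highest mean after an increase against the lowest mean without one, in different ≤35 kg subgroups.
- *That only the starting dose follows weight.* The raised levels are also set by weight band, and weight change permits later adjustment. What weight does not determine is who is increased.
- *That the SAP reduces everything to one column.* The one-column sentence sits in the section on Period 1 displays. The SAP's synopsis still calls for by-dose output, and Table 14.3.11 is by dose. Three adverse event table titles also mention a treatment group, but the SAP defines none. The SAP is inconsistent rather than uniformly pooled, and by-dose adverse event tables were already missing from Section 8.1.1 and the table list. The Note adds the exposure rationale and drops the period split.
- *That a safety signal has been averaged away.* No signal is documented, the number of patients increased is unknown, and patient-level listings of adverse events, skin examinations and drug application remain planned.

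It is also fair to say that the study is exploratory, has about 20 patients and no dose comparison among its objectives, and that the protocol itself asks for an overall adverse event tabulation. By-dose cells would be small: 3 events among 6 increased patients would be 50% with an exact 95% interval of about 12–88%. Dose is confounded with non-response and with time on treatment. These points argue for descriptive tables only, which is what the protocol planned. They do not support the exposure statement.

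**Conclusion.** The concern holds in a limited form. The statement that exposure is consistent across doses is not supported by the modelling in these documents, which reports similarity to adults for the starting doses only. Under the protocol's own proportionality assumption, a Week 6 increase means 2.0-fold higher exposure at ≤35 kg and 1.5-fold above 35 kg. These are simulated group means, with no between-patient spread given. Pooling can therefore dilute dose-related tolerability findings on the primary objective; whether it did cannot be known from the plan.

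Separately, and without any modelling assumption, SAP Section 8 and the table list omit displays that Protocol Section 13.5 and the SAP's synopsis specify. The SAP's two statements on CBD levels disagree, and Section 10 discloses no change. Nothing here bears on whether the doses themselves were appropriate.

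**What to change.** 1. Withdraw the exposure sentence in the Note, or limit it to the starting doses, and state that the Week 6 increase was triggered by response.
2. Keep the pooled ZYN002 column as the total.
3. Restore, as descriptive displays, the protocol's adverse events by dose at onset, skin scores by dose at assessment, and laboratory results by treatment at assessment. Showing patient-time at each dose would help, but that is an addition to the protocol's tables.
4. Produce Table 14.3.11 by dose and weight group, set against the simulated exposures that the synopsis promises, and bring SAP Section 8.1.12 into line with it.
5. Disclose any remaining departure from the protocol in a corrected Note or in the study report. Rewriting Section 10 of the 2022 SAP is not necessary.

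The cost is a few descriptive tables. First confirm that dose at adverse event onset can be recovered from the drug application records, because the Note says that data were collected, not merely summarised, as a single arm. The drawback is small cells and confounding of dose with non-response and time, so the tables should carry that caveat and no inference should be drawn from them.
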